8.6. Relationship

The relationship of an AE to the administration of the study drug is to be assessed by the investigator according to the following definitions:

- No (unrelated, not related, no relation): The time course between the administration of study drug and the occurrence or worsening of the AE rules out a causal relationship and another cause (concomitant drugs, therapies, complications, etc.) is suspected.
- Yes (related): The time course between the administration of study drug and the occurrence or worsening of the AE is consistent with a causal relationship and no other cause (concomitant drugs, therapies, complications, etc.) can be identified.

The following factors should also be considered:

- The temporal sequence from study drug administration The event should occur after the study drug is given. The length of time from study drug exposure to event should be evaluated in the clinical context of the event.
- Underlying, concomitant, intercurrent diseases Each report should be evaluated in the context of the natural history and course of the disease being treated and any other disease the participant may have.
- Concomitant medication The other medications the participant is taking or the treatment the participant receives should be examined to determine whether any of them might be recognized to cause the event in question.
- Known response pattern for this class of study drug Clinical and/or preclinical data may indicate whether a particular response is likely to be a class effect.
- Exposure to physical and/or mental stresses The exposure to stress might induce adverse changes in the recipient and provide a logical and better explanation for the event.
- The pharmacology and PK of the study drug The known pharmacologic properties (absorption, distribution, metabolism, and excretion) of the study drug should be considered.

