6.2.6. Analysis of Adverse Event Data

Analysis of AE data will primarily be descriptive based on the DAIDS table for Grading the Severity of Adult and Pediatric Adverse Events, July 2017, version 2.1. Adverse events will be coded using the Medical Dictionary for Regulatory Activities (MedDRA). An AE is considered treatment-emergent if it begins or worsens in severity after the first dose of randomized study drug. The number and percentage of participants with treatment-emergent AEs will be tabulated by system organ class (SOC) and preferred term. Additional AE summaries will be provided by severity, drug related AEs, AEs leading to study drug discontinuation, and serious AEs.

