8.10.3.1. Expedited IND Safety Reports to the FDA

All reporting to the FDA will be completed by the IND sponsor.

7 Calendar-Day Telephone or Fax Report:

The IND sponsor is required to notify the FDA of any fatal or life-threatening AE that is unexpected and assessed by the investigator to be possibly related to the investigational agent. Such reports are to be submitted to the FDA within 7 calendar days of first learning of the event. Follow-up information will be submitted to the FDA as soon as relevant information is available.

15 Calendar-Day Written Report:

The IND sponsor is required to notify the FDA of any SAE that is unexpected and related to the investigational agent in a written IND Safety Report.

Written IND Safety Reports should include an Analysis of Similar Events in accordance with regulation 21 CFR § 312.32. All safety reports previously filed with the IND concerning similar events should be analyzed. The new report should contain comments on the significance of the new event considering the previous, similar reports.

Version: 7.0 18 May 2021

Written IND safety reports with Analysis of Similar Events are to be submitted to the FDA within 15 calendar days of first learning of the event. Follow-up information will be submitted to the FDA as soon as relevant information is available.

IND Annual Reports:

In accordance with the regulation 21 CFR § 312.33, the IND sponsor shall within 60 days of the anniversary date that the IND went into effect submit a brief report of the AEs and progress of the investigation. Please refer to Code of Federal Regulations, 21 CFR § 312.33 for a list of the elements required for the annual report. All IND annual reports will be submitted to the FDA by the IND sponsor.

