9.2. Stopping Criteria for the Study

The study enrollment and dosing will be stopped, and an ad hoc review will be performed if any of the specific following events occur or, if in the judgment of the study physician, participant safety is at risk of being compromised:

- I. Unexpected death of a dosed participant.
- II. Occurrence of a life-threatening allergic/hypersensitivity reaction (anaphylaxis), manifested by bronchospasm with or without urticaria or angioedema requiring hemodynamic support with pressor medications or mechanical ventilation.
- III. A trend of unexpected SAEs related to the study product.
- IV. Two participants with a Grade 3 or higher lab toxicity for the same parameter associated with the study product.
- V. An overall pattern of symptomatic, clinical, or laboratory events that the SRC considers associated with study product and that may appear minor in terms of individual events but that collectively may represent a serious potential concern for safety.
- VI. Any other event(s) which is considered to be a SAE in the good clinical judgment of the responsible physician. This will be appropriately documented.

Upon completion of this review, the SRC will determine if the study enrollment or study dosing should be interrupted or if study enrollment and study dosing may continue according to the protocol. Should the trial not be stopped at this time point, the final analysis would need to account for the number of interim analyses that were conducted. Therefore, we will use the O'Brien and Flemming type spending function to preserve the overall Type 1 error. This will

Version: 7.0

Version: 7.0 18 May 2021

allow for stopping the trial earlier should the intervention arm be shown to be superior at an interim analysis.

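### The two relatedness classes in section 8.6 are not exhaustive: an adverse event with compatible timing and another identifiable cause belongs to neither

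*Protocol*

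**What the plan says.** Section 8.6 states that the relationship of an adverse event to study drug "is to be assessed by the investigator according to the following definitions", and then gives two definitions, No and Yes.

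- **No:** the time course "rules out a causal relationship and another cause (concomitant drugs, therapies, complications, etc.) is suspected".
- **Yes:** the time course "is consistent with a causal relationship and no other cause (concomitant drugs, therapies, complications, etc.) can be identified".

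The section continues with "The following factors should also be considered" and lists timing, concurrent disease, concomitant medication, class effects, stress and pharmacology. It gives no third class, default or tie-break.

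The classification is then used elsewhere:

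- Section 6.2.6: "Additional AE summaries will be provided by severity, drug related AEs", among others.
- Section 9.2, stopping criterion III: "A trend of unexpected SAEs related to the study product". Criterion IV speaks of laboratory toxicity associated with the product.
- Section 8.9: expedited safety reports to investigators, for unexpected and related SAEs.
- Section 8.10.3.1: the 15-day FDA report uses related. The 7-day report covers unexpected fatal or life-threatening events "assessed by the investigator to be possibly related to the investigational agent".
- Section 8.10: follow-up beyond 28 days depends on the event being related.
- Section 4.8: a severe or life-threatening drug-related AE is a discontinuation criterion.

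**The concern.** Each definition joins two conditions with *and*, and the two are not complements of each other. An event that meets one half of each definition has no class. The pattern that falls through is an ordinary one here. Participants are inpatients with acute COVID-19, section 4.7 permits remdesivir and corticosteroids, and dosing lasts about five days during the acute illness. The events that section 8.3 already attributes to the drug (insomnia, headache, nausea, vomiting, abdominal pain, loose stools) are ones for which the illness or another medicine can readily be named as a cause.

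At stake is the consistency of every output that depends on the relatedness call. Site investigators make that call when they report the event, so an analysis plan cannot recover it afterwards. Separately, the 7-day reporting rule depends on a judgement that the two-level scale cannot record.

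**Working it through.** No figure in the plan bears on this point, so the check is a comparison of the definitions.

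**Step 1. Two by two.** Treat timing as either ruling out or consistent with causation, and another cause as either present or absent. Apply both definitions literally.

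| Timing | Another cause | Meets No? | Meets Yes? | Class |
|---|---|---|---|---|
| Rules out | Present | yes | no | No |
| Rules out | Absent | no (needs a suspected cause) | no (timing) | none |
| Consistent | Present | no (timing) | no (other cause) | none |
| Consistent | Absent | no | yes | Yes |

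Two of the four combinations are classified and 4 − 2 = 2 are not.

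**Step 2. Allow for the difference in wording.** No asks for a cause that is *suspected*; Yes fails only if one *can be identified*. Split another cause into three levels: none suspected, suspected but not identifiable, and identifiable. That gives 2 × 3 = 6 combinations.

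- Rules out: none suspected gives no class; suspected gives No; identifiable gives No.
- Consistent: none suspected gives Yes; suspected only can be read as Yes; identifiable gives no class.

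Two of the six remain without a class. The gap is narrower than in step 1, but it is strict wherever another cause can be identified and timing is compatible.

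**Step 3. Do the listed factors close it?** They direct the investigator to concurrent disease, concomitant medication and stress. Finding a cause there removes Yes by its own wording. No stays unavailable, because its timing condition ("The time course between the administration of study drug and the occurrence or worsening of the AE rules out a causal relationship") is not met. The factors inform judgement without assigning a class.

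**Step 4. Terms in use.** Section 8.6 has related and unrelated. Section 8.10.3.1 uses related for the 15-day report and possibly related for the 7-day report. The second term has no definition in 8.6.

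**Step 5. Which rules are exposed?**

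| Depends on relatedness | Does not |
|---|---|
| Drug-related AE summary (6.2.6) | Treatment-emergent AE tables and SAE summary (6.2.6) |
| Expedited reports (8.9, 8.10.3.1) | 24-hour notification of all SAEs (8.10.3) |
| Follow-up of related AEs (8.10) | Primary safety endpoints (1.2) |
| Related-AE discontinuation criterion (4.8) | Stopping criteria I, II and VI (9.2) |
| Stopping criterion III (9.2); possibly IV, through *associated with* | |

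**The case against.** The strongest reply is that little of the safety evaluation rests on relatedness. The primary safety endpoints in section 1.2 carry no relatedness condition, the main AE table counts all treatment-emergent events, and the trial is randomised and double-blind. The between-arm comparison of all events is therefore sound whatever section 8.6 says. All SAEs are notified within 24 hours regardless of relationship. The looser wording of the 7-day rule, although inconsistent, works against under-reporting. Section 9.2 also allows a stop on the study physician's judgement, and section 4.8 allows discontinuation on the investigator's opinion. All of this stands, and it limits the reach of the point.

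A second reply is that the listed factors show judgement was intended, so investigators will record an answer anyway. They will, but the protocol does not tell them which, and two careful investigators can differ on the same event.

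A reader might go further and infer that the rule biases the primary safety objective towards finding no signal, because an identifiable other cause always bars Yes. The text does not support that. Compatible timing equally bars No, so the event is unclassified and not counted as unrelated by rule. An investigator could resolve it either way, so no direction follows. Nor can one say what share of events is affected, since the protocol gives no such figure.

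**Conclusion.** The point holds as a defect in a stated definition. The two classes in section 8.6 leave two of four combinations of timing and other cause without a class (two of six on the finer reading), and nothing elsewhere in the protocol closes the gap. The 7-day report also depends on a grade that the scale lacks. The consequence is undefined classification that may differ between investigators and sites, in the outputs and triggers that depend on relatedness. The all-causality safety comparison is untouched.

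Two assumptions enter. The first is that the definitions are applied as written, which section 8.6 asks for. The second is that compatible timing with an identifiable other cause is common. That is a judgement from the population and permitted medicines; the logical gap does not depend on it. Whether stopping criterion IV is affected depends on whether *associated with* means the 8.6 class, which the protocol does not say. The point is worth correcting, but it does not touch the primary efficacy analysis.

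**What to change.** Make the classes in section 8.6 complementary. For example, related: a reasonable possibility that the study drug caused the event, even if other causes are possible; not related: no reasonable possibility. Keep the listed factors as guidance for that judgement. In section 8.10.3.1, replace possibly related with the defined term. In sections 4.8, 6.2.6, 8.9, 8.10 and 9.2, tie related to the same definition, and state whether *associated with* in stopping criterion IV means the same. How the discontinuation and stopping criteria should operate under the clarified term is for the sponsor and safety committee to confirm; this point asks only that the passages be reconciled.

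The cost is a wording amendment, site retraining and more events classed as related. There is also a statistical cost. Parts are enrolled in sequence, 200 mg appears by name only in Part 1 and 800 mg only from Part 3, and placebo is pooled across parts (sections 4.2 and 6.2.2). A definition changed partway would differ by part and so by dose, and would be mixed within the pooled placebo group. Events already assessed should therefore be reassessed under the new wording, preferably while still blinded, or the drug-related summary should be flagged as resting on two definitions.

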8.7. Assessment of Grade/Severity

The investigator will assess grade for each AE and SAE reported during the study, which will be recorded in the CRF. The assessment will be based on the DAIDS AE Grading Table, corrected Version 2.1, July 2017, which is available on the DAIDS RSC website at https://rsc.niaid.nih.gov/clinical-research-sites/daids-adverse-event-grading-tables.

Any AE that changes in grade during its course will be recorded in the CRF at the highest level experience by the participant.

8.8. Expectedness

Unexpected adverse event: An AE, which varies in nature, intensity or frequency from information on the investigational drug/agent provided in the IB, package insert or safety reports. Any AE that is not included in the informed consent is considered "unexpected". At the time of this protocol, no events are considered to be expected for safety reporting purposes.

Expected (known) adverse event: An AE, which has been reported in the package insert. An AE is considered "expected", only if it is included in the informed consent document as a risk.

8.9. Handling of Expedited Safety Reports

In accordance with local regulations, the IND sponsor or designee will notify investigators of all SAEs that are unexpected (i.e., not previously described in the IB), and related to EIDD-2801. This notification will be in the form of an expedited safety report (ESR) that is to be emailed to the investigators and the study coordinators. Upon receiving such notices, the investigator must review and retain the notice with the IB and where required by local regulations, the investigator will submit the ESR to the appropriate IRB. The investigator and IRB will determine if the informed consent requires revision. The investigator should also comply with the IRB procedures for reporting any other safety information.

8.10. Reporting

Information about all AEs, whether volunteered by the participant, discovered by investigator questioning, or detected through physical examination, laboratory test or other means, will be collected, recorded, and followed as appropriate.

All AEs experienced by participants will be collected and reported from the first dose of EIDD-2801, throughout the study, and will only be followed for 28 days unless related to the investigational agent.

Participants who have an ongoing AE related to the study procedures and/or medication(s) may continue to be periodically contacted by a member of the study staff until the event is resolved or determined to be irreversible by the investigator.

Version: 7.0

8.10.1. Routine Adverse Event Reporting

If an ongoing AE changes in its intensity or in its perceived relationship to investigational product, the maximum severity of the AE will be recorded. Adverse events should be followed to resolution or stabilization or reported as SAEs if they become serious. Follow-up is also required for AEs that cause interruption or discontinuation of investigational product, or those that are present at the end of study participation. Participants with AEs at study completion should receive post-treatment follow-up as appropriate.

All identified non-serious AEs must be recorded and described on the appropriate Adverse Event Case Report Form (CRF).

8.10.2. Laboratory Test Abnormalities

Laboratory abnormalities present at the screening visit will be recorded as pre-treatment signs and symptoms. After study treatment administration, all grade 3 and 4 clinical laboratory results that represent an increase in severity from baseline will be reported as AEs. A grade 1 or 2 clinical laboratory abnormality should be reported as an AE only if it is considered clinically significant by the investigator.

In addition, the following laboratory abnormalities should also be captured on the AE CRF page as appropriate:

- Any laboratory test result that is clinically significant or meets the definition of an SAE
- Any laboratory abnormality that required the participant to have the investigational product discontinued or interrupted
- Any laboratory abnormality that required the participant to receive specific corrective therapy

It is expected that wherever possible, the clinical, rather than the laboratory term would be used by the reporting investigator (e.g., anemia versus low hemoglobin value).

8.10.3. Serious Adverse Event Reporting

All SAEs (including deaths) occurring from the first dose of the study drug through the 28 day End-of-Study telephone call will be collected and recorded on the Adverse Event Case Report Form (CRF).

The PI or clinical site personnel should notify of all SAEs, regardless of relationship to the investigational drug, within 24 hours of clinical site personnel becoming aware of the event. The PI (or designee) will provide the initial notification by sending a completed SAE form which must include the PI's (or designee's) assessment of the relationship of the event to investigational drug and must be signed by the PI. Follow-up information, or new information regarding an ongoing SAE, must be provided promptly to at or via fax.

Version: 7.0

The SAE Form will collect data surrounding the event (e.g., the nature of the symptom[s], time of onset in relation to initiation of therapy, duration, intensity, and whether or not therapy was interrupted or discontinued). The Investigator's assessment of the probable cause of the event will also be included. In addition, relevant medical history, concomitant medications, laboratory and diagnostic tests reports, and procedures as well as all pertinent medical information related to the event will also be collected.

SAEs will be reported to each participating site's IRB per institutional guidelines by the PI.

After the initial SAE report, the investigator is required to proactively follow each participant and provide further information regarding the participant's condition.

All AE(s) and SAE(s) will be followed until one of the following conditions is met:

- Resolution
- The condition stabilizes
- The event is otherwise explained
- The participant is lost to follow-up
- Death

8.10.3.1. Expedited IND Safety Reports to the FDA

All reporting to the FDA will be completed by the IND sponsor.

7 Calendar-Day Telephone or Fax Report:

The IND sponsor is required to notify the FDA of any fatal or life-threatening AE that is unexpected and assessed by the investigator to be possibly related to the investigational agent. Such reports are to be submitted to the FDA within 7 calendar days of first learning of the event. Follow-up information will be submitted to the FDA as soon as relevant information is available.

15 Calendar-Day Written Report:

The IND sponsor is required to notify the FDA of any SAE that is unexpected and related to the investigational agent in a written IND Safety Report.

Written IND Safety Reports should include an Analysis of Similar Events in accordance with regulation 21 CFR § 312.32. All safety reports previously filed with the IND concerning similar events should be analyzed. The new report should contain comments on the significance of the new event considering the previous, similar reports.

Version: 7.0 18 May 2021

Written IND safety reports with Analysis of Similar Events are to be submitted to the FDA within 15 calendar days of first learning of the event. Follow-up information will be submitted to the FDA as soon as relevant information is available.

IND Annual Reports:

In accordance with the regulation 21 CFR § 312.33, the IND sponsor shall within 60 days of the anniversary date that the IND went into effect submit a brief report of the AEs and progress of the investigation. Please refer to Code of Federal Regulations, 21 CFR § 312.33 for a list of the elements required for the annual report. All IND annual reports will be submitted to the FDA by the IND sponsor.

8.10.4. Pregnancy and Exposure During Breastfeeding

If a pregnancy is reported, the investigator will record pregnancy information on the appropriate form and submit it to the sponsor within 24 hours of learning of the pregnancy in a female participant or female partner of male participant (after obtaining the necessary signed informed consent from the female partner).

Although pregnancy and infant exposure during breastfeeding are not considered AEs, any pregnancy or infant exposure during breastfeeding in a participant (spontaneously reported to the investigator or their designee), including the pregnancy of a male participant's female partner, that occurs during the study are reportable to the Sponsor.

All reported pregnancies must be followed to the completion/termination of the pregnancy.

Any pregnancy complication will be reported as an AE or SAE.

The medical reason (example: maternal health or fetal disease) for an elective termination of a pregnancy will be reported as an AE or SAE. Prenatal testing showing a fetus will be born with severe abnormalities/congenital anomalies that leads to an elective termination of a pregnancy will be reported as an SAE for the fetus.

Pregnancy outcomes of ectopic pregnancy, spontaneous abortion, missed abortion, benign hydatidiform mole, blighted ovum, fetal death, intrauterine death, miscarriage, and stillbirth must be reported as serious events (Important Medical Events). If the pregnancy continues to term, the outcome (health of infant) must also be reported

